### **3. PARTICIPANT SELECTION AND ENROLLMENT PROCEDURES**

#### **3.1 Inclusion Criteria**

- Biopsy proven prostate adenocarcinoma
- Rising PSA after definitive therapy with prostatectomy or radiation therapy (external beam or brachytherapy)
  - a. Post radical prostatectomy (RP) – AUA recommendation (39)
    - i. PSA greater than 0.2 ng/mL measured after at least 6 weeks from radical prostatectomy
    - ii. Confirmatory persistent PSA greater than 0.2 ng/mL (total of two PSA measurements greater than 0.2 ng/mL)
  - b. Post-radiation therapy –ASTRO-Phoenix consensus definition (40)
    - i. A rise of PSA measurement of 2 or more ng/mL over the nadir
- Able to provide written consent
- Karnofsky performance status of  $\geq 50$  (or ECOG/WHO equivalent)

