#### **11.4 Key variables**

Reference standard: disease status of a lesion will be defined by biopsy of suspicious lesions, when clinically feasible. 12-months clinical follow-up with imaging will be gold standard if biopsy cannot be done.

Test to be evaluated:  $^{68}\text{Ga}$ -NeoBOMB1 and  $^{68}\text{Ga}$ -PSMA R2 positivity will be determined by the operator as uptake more than the adjacent background (malignant) or less (benign). Visual conspicuity against background on the diffusion weighted images and presence of an anatomically corresponding abnormality on the T1w and T2w images are the criteria for detecting a lesion on MRI.

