##### **11.4.1 Analysis Population**

All lesions identified by  $^{68}\text{Ga}$ -NeoBOMB1 PET/MRI and  $^{68}\text{Ga}$ -PSMA R2 PET/MRI.

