##### **11.4.2 Analysis Plan**

- Sensitivity, specificity, and positive and negative predictive value of imaging modalities will be estimated.
- Sensitivity and specificity of PET/MRI and MR alone will be compared by McNemar tests of paired proportions.
- The number and type of discrepancies between  $^{68}\text{Ga}$ -NeoBOMB1 and  $^{68}\text{Ga}$ -PSMA R2 will be tabulated.
- We will explore hypotheses about the reasons for such discrepancies, such as PSA level/velocity, Gleason score, and location.

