#### **11.5 Sample size justification**

The following estimate is for a per-lesion analysis. We expect approximately 70% of patients (~35) to have one or more PET-positive findings and approximately 1/3 to be biopsied. Our existing data for  $^{68}\text{Ga}$  PSMA-11 and  $^{68}\text{Ga}$ -RM2 (please see attached publications) indicate no false positive findings based on biopsy. We cannot predict an average number of lesions per patient given small data available to date, but if only half of the positive patients have more than one lesion, this will easily yield 50 lesions. We also expect the sensitivity of MR alone to be roughly 40%, while that of PET to be roughly 60% or more. A sample size of 50 patients will provide 90% power at one-sided 5% error to detect such a difference. Participants who complete only one PET/MRI scan (either due to withdrawal of consent or loss to follow-up) will not be replaced with additional subjects.

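### Section 11.4.2 promises specificity, NPV and a McNemar test of specificity, but no negative unit is defined, so lesion-level specificity and NPV cannot be validly estimated and the test is tilted against PET

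*Combined protocol and SAP*

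**What the plan says.** Section 11.4.2 lists four accuracy measures: "Sensitivity, specificity, and positive and negative predictive value of imaging modalities will be estimated". It then adds a comparative test: "Sensitivity and specificity of PET/MRI and MR alone will be compared by McNemar tests of paired proportions".

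The sections that fix the units and the reference standard are these:

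- **Analysis set (11.4.1):** "All lesions identified by" the two tracer PET/MRI scans. I read this as lesions found on either scan.
- **Unit (11.5):** "The following estimate is for a per-lesion analysis".
- **Reference standard (11.4):** "disease status of a lesion will be defined by biopsy of suspicious lesions, when clinically feasible"; otherwise "12-months clinical follow-up with imaging will be gold standard if biopsy cannot be done". Under 6.3 the follow-up is chart review of whatever standard-care biopsies and imaging took place.
- **Population (3.1):** only men whose PSA meets a biochemical-recurrence definition after prostatectomy or radiation.
- **Declared outcomes:** the primary outcome is lesions detected per patient for each imaging method (10.1). The secondary outcome is the percentage of detected lesions confirmed malignant, that is, PPV (10.4).

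No section lists anatomical sites to be scored as negative, or says when a participant counts as disease-free.

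**The concern.** Specificity and NPV need units that could be negative, chosen without regard to the test result, with a reference standard applied to them. Here a site becomes a unit because a scan drew attention to it. Sites that are quiet on every read, which would form most of a specificity denominator, never enter.

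Moving to the patient level does not help. Section 11.5 expects about 35 of 50 men to be PET-positive, which leaves about 15 PET-negative. All of them entered with biochemical recurrence, and no rule allows a negative scan with unremarkable follow-up to count as a true negative.

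The comparison with MR alone is the principal goal in 10.1. A specificity result in which PET looks worse than MR could arise purely from how lesions were selected, and could be read as a finding about the tracers.

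**Working it through.** **1. The plan's own figure.** Section 11.5 gives 90% power for sensitivity of 60% (PET) against 40% (MR), n = 50, one-sided 5%. A one-sample test against a fixed 40% reproduces it:

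Φ(0.20/√(0.24/50) − 1.645) = Φ(2.887 − 1.645) = 89.3%.

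As a McNemar test, power is Φ((0.20√50 − 1.645√ψ)/√(ψ − 0.04)), where ψ is the discordant share. This gives 90% at ψ ≈ 0.25 and 62.9% at ψ = 0.52 (independent reads: 0.6×0.6 + 0.4×0.4). The plan does not state ψ. Either way the figure concerns sensitivity, and no figure is given for specificity or NPV.

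**2. Tracers pooled, set taken as tracer-positive lesions.** Every unit is PET-positive, so TN = FN = 0. Specificity = 0/(0 + FP), which is 0% or, with no false positives, undefined. NPV = 0/0.

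**3. One tracer at a time.** A benign lesion negative on tracer A is in the set only because tracer B was falsely positive. Assume independent reads and the same true specificity s for A, B and MR. Among benign lesions positive on A or B:

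- apparent specificity of A = s(1 − s)/(1 − s²) = s/(1 + s);
- apparent specificity of MR = s.

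**4. The McNemar comparison of one tracer with MR.** Under the same assumptions, benign A+/MR− lesions occur with probability (1 − s)s and all enter the set. Benign A−/MR+ lesions enter only if B is also positive, with probability s(1 − s)(1 − s). The share of discordant benign lesions counting against PET is therefore 1/(1 + (1 − s)) = 1/(2 − s), when it should be one half.

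| True s (all reads) | Apparent specificity, one tracer | Apparent specificity, MR | Discordant share against PET |
|---|---|---|---|
| 0.80 | 0.44 | 0.80 | 0.83 |
| 0.90 | 0.47 | 0.90 | 0.91 |
| 0.95 | 0.49 | 0.95 | 0.95 |
| 0.99 | 0.50 | 0.99 | 0.99 |

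If lesions positive on MR only are added, A+/MR− and A−/MR+ each have probability s(1 − s), and the share returns to one half. The double-negative cell is still missing, but McNemar does not use it.

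**5. How many benign lesions there may be.** Section 11.5 expects 50 lesions. PPV for these tracers is not given, so I assume a range: 100% gives 0 benign lesions, 95% gives 2.5, 90% gives 5 and 80% gives 10. The sidedness of the specificity test is not stated. An exact one-sided 5% test needs at least 5 discordant lesions all in one direction (0.5⁵ = 0.031; 0.5⁴ = 0.0625).

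**6. What the pooled test would do under step 2.** Every discordant benign lesion counts against PET. With 5 benign lesions, an exact one-sided test in that direction declares PET worse with probability s⁵: 0.59 at s = 0.90 and 0.77 at s = 0.95. With 10 benign lesions the probability is about 1.0 at either value, although each tracer's true specificity equals MR's.

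**The case against.** **The set may not be all tracer-positive.** A reader might infer that true negatives are zero whatever the data. The documents do not support that as a certainty. It needs two readings that the plan does not state: that the tracers are pooled, and that a lesion identified by PET/MRI means one with tracer uptake. PET/MRI contains an MR component, 11.4 allows a PET result below background to be called benign, and 10.1 and 10.4 report by imaging method. Section 11.5 also expects PET sensitivity of roughly 60%, whereas a pooled tracer-positive set would force 100%. This objection stands, so nominal true negatives are possible. They still exist only where another read was falsely positive, and sites quiet on every read are still not counted.

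**The plan does not forecast zero benign lesions.** A reader might infer that it does, because 11.5 says existing data "indicate no false positive findings based on biopsy". Those data concern two other tracers and biopsy only. In this trial about one third are expected to be biopsied, and the rest fall to 12-month imaging. The objection stands: few benign lesions are plausible, but none is not a plan assumption.

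**McNemar does not need true negatives.** It uses only discordant lesions. A reader might infer that the comparison is beyond rescue, but adding verified MR-only lesions would allow a valid relative comparison of false positives. This stands and shapes the fix.

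**Little depends on these measures.** The primary outcome, the secondary outcome, the power statement and the interim rule in 11.3 do not use specificity or NPV. This also stands and limits the weight of the point.

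**Conclusion.** The concern holds in a limited form. Absolute lesion-level specificity and NPV are not validly estimable, because the units are selected by scan findings and no negative unit is defined. That conclusion does not depend on which reading of 11.4.1 is taken. Patient-level specificity is not estimable either, since every participant has biochemical recurrence and no rule defines disease-free status.

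The McNemar comparison of specificity is biased against PET to the extent that benign lesions seen only on MR alone are left out. On the tracer-positive reading, with independent reads and equal specificity of 0.80 to 0.99, 83% to 99% of discordant benign lesions would count against a single tracer. These sizes are illustrative: the specificity values, the independence of reads and the PPV range are assumptions, not figures from the plan. The 0% or undefined result applies only if the tracers are pooled and the set means tracer-positive lesions.

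This should be fixed before analysis. It does not invalidate the declared outcomes, because lesion counts and PPV need no true negatives.

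**What to change.** - **11.4.2, accuracy measures:** delete lesion-level specificity and NPV. Report detection and PPV for each imaging method. State that patient-level specificity is not estimable because all participants have biochemical recurrence.
- **11.4.2, McNemar test of specificity:** choose one of two routes. Either delete it, or extend 11.4.1 to all lesions positive on any read (NeoBOMB1, PSMA R2 or MR) and restate the test as a paired comparison of false-positive lesions, each tracer against MR, with an analysis that allows for several lesions in one participant. Report the number of verified benign lesions beside the result.
- **Optional:** add a predefined region-level table, with each region scored positive or negative on every blinded read. Estimate specificity and NPV over verified regions only, with intervals clustered by participant, and report how many negative regions were verified. Five regions, for example, would give at most 50 × 5 = 250 units. That is a ceiling, since only regions with biopsy or follow-up imaging count.

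The cost is wording in 11.4.1 and 11.4.2 and, for the optional table, a region list on the read form; 10.2 already records the location of uptake. The trial can make fewer accuracy claims. Region-level figures would be coarser than lesion-level ones. They would also be subject to partial verification, because 6.3 relies on standard-care records, and the same limit applies to MR-only lesions in the restated comparison.

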### **5.3 Details of image analysis**

The PET/MRI scans will be interpreted by ABNM certified Nuclear Medicine physicians and an ABR certified Radiologists. Drs [name], [name], [name], and [name] have significant clinical experience and will be blinded to the participants' medical history and the results of other imaging modalities. Consensus read will be obtained for each scan. Each lesion will be tabulated and a comparison of lesion detection by each scanner will be conducted.

The study team will communicate the results of the scans to the referring (treating) physicians who can decide what to do with the findings, including making treatment decisions.

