## **10.2 Measurement Methods**

PET images will be interpreted using the AW software (GE Healthcare) and the location of uptake will be recorded for each patient, blinded to the results of other studies. MR images will be evaluated for detection of areas of abnormal signal or anatomical structures, blinded to the results of PET or other studies.

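### The index test in the only formal comparison is inconsistently defined: some sections name the PET/MRI read, others an uptake-only PET call, and the sensitivity result depends on which is used

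*Combined protocol and SAP*

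**What the plan says.** All references are to the combined protocol and SAP.

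**Sections that name the PET/MRI read.** Section 10.1 sets the principal goal as PET/MRI with each tracer against MR alone. Section 11.4.2 supplies the only hypothesis test: "Sensitivity and specificity of PET/MRI and MR alone will be compared by McNemar tests of paired proportions". The tracer-against-tracer comparison is only tabulated. Section 11.1 pairs an MRI evaluation with a PET/MRI evaluation, and Section 5.3 treats the combined scan as the thing read: "The PET/MRI scans will be interpreted by ABNM certified Nuclear Medicine physicians and an ABR certified Radiologists".

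**Sections that describe an uptake-only call.** Section 11.4 says that tracer "positivity will be determined by the operator as uptake more than the adjacent background (malignant) or less (benign", and gives MRI its own separate criteria (diffusion, T1w and T2w). Section 10.2 says "PET images will be interpreted using the AW software (GE Healthcare) and the location of uptake will be recorded for each patient" and has MR read blinded to PET. Section 11.5 plans on PET, not PET/MRI: "We also expect the sensitivity of MR alone to be roughly 40%, while that of PET to be roughly 60% or more".

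No section says how uptake and MR findings combine into a PET/MRI result. Section 11.4.1 limits the analysis set to lesions identified by the two PET/MRI scans.

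**The concern.** MR is a component of PET/MRI. If the combined read enters the McNemar test and MR findings count toward it, a malignant lesion seen on MR is also, wholly or largely, a PET/MRI lesion. The cell that should count against PET/MRI is then empty or nearly so. The sensitivity comparison would lean toward PET/MRI by construction, and a significant result would say little about the tracer. If the uptake call is tested instead, the comparison is a fair contest in principle, but the stated conclusion is about PET/MRI, which is not what was measured or powered. The same images could support opposite conclusions, depending on a choice that the plan leaves open.

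**Working it through.** **Inputs.** From Section 11.5: 50 units, MR 40%, PET 60%, one-sided 5%, stated power 90%. That section opens "The following estimate is for a per-lesion analysis", expects that PET-positive men "this will easily yield 50 lesions", and then states power for 50 patients; I use 50 malignant lesions. Assumed, because the documents do not say: lesions are independent, and PET hits are independent of MR hits unless varied below. Write b for the share of malignant lesions that only the index test finds, and c for the share that only MR finds.

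**1. The plan's 90%.** A one-sample test of 60% against a fixed 40% gives Φ(0.20×√50/√0.24 − 1.645) = Φ(2.887 − 1.645) = 89.3%. The figure is recovered, but with MR treated as a known constant and not as the paired arm of Section 11.4.2.

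**2. The paired test on the uptake call, 60% against 40%.** With d = b − c = 0.20 and ψ = b + c, approximate power is Φ((d√n − 1.645√ψ)/√(ψ − d²)). Under independence b = 0.6×0.6 = 0.36, c = 0.4×0.4 = 0.16 and ψ = 0.52, so power = Φ((1.414 − 1.186)/√0.48) = Φ(0.329) = 62.9%.

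| MR-only share c | Approximate power | Exact power |
|---|---|---|
| 0% | 95.5% | 98.2% |
| 5% | 84.3% | 80.7% |
| 10% | 73.3% | 67.9% |
| 16% (independent) | 62.9% | 56.6% |

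Power is 90% only if c is about 2.6% (approximate) or 2.0% (exact). Under independence, about 108 lesions are needed for 90% by the approximation.

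**3. A full either-positive read.** Here c = 0. With b-type lesions unopposed, the exact one-sided p is 0.5 to the power of their number: four give 0.0625 and five give 0.031. The test therefore rejects when PET adds five or more lesions, with the count distributed Bin(50, PET sensitivity × 0.6).

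| PET sensitivity (MR 40%) | Uptake call against MR rejects | Either-positive read against MR rejects |
|---|---|---|
| 20% | <0.1% | 73% |
| 40% | 3.3% | 99.7% |
| 60% | 57% | >99.9% |

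**4. A partial version.** Suppose readers discount a fraction f of MR-only lesions, so that c = f × 0.4 × (1 − PET sensitivity).
- PET 40%: b = 0.24. For f = 10%, 25% and 50%, c = 0.024, 0.06 and 0.12, and PET/MRI wins 92%, 71% and 33% of the time. With f = 100% this is the uptake test again, at 3.3%.
- PET 20%: b = 0.12. For f = 10% and 25%, c = 0.032 and 0.08, and the win rate falls from 73% to 33% and 9%.

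**5. More overlap between PET and MR.** Under a full either-positive read, the win rate is 10%, 57%, 89% or 98% if PET adds 5%, 10%, 15% or 20% of lesions.

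**6. What the 60% describes.** With PET 60% and MR 40%, an either-positive read has sensitivity 60% if MR hits lie wholly within PET hits, 1 − 0.6×0.4 = 76% if independent, and 100% if disjoint. The planning value is a PET figure and equals a PET/MRI figure only in the first case.

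**7. Specificity.** Among non-malignant lesions, an either-positive read keeps every MR false positive and may add PET ones, so it can only tie with or lose to MR.

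**The case against.** The strongest reply is that Section 11.4, read literally, already settles the matter: the test to be evaluated is uptake against background, and an MR abnormality without uptake is index-negative. Sections 10.2 and 11.5 agree, and PET/MRI may simply be the name of the examination. A consensus read is not an either-positive rule, and no passage states one. This much stands: a reader might infer that PET/MRI is bound to win, and the documents do not support that. The inference needs a combining rule that the plan does not contain. Even under a full rule at least five unopposed lesions are required, and the win rate drops sharply if PET adds few lesions.

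A reader might also infer that the tilt covers the whole of the Section 11.4.2 test and both tracers. It does not. Specificity moves the other way. One of the two sessions acquires only attenuation-correction MR, so the diagnostic MR of Section 11.4 is not fully contained in that PET/MRI scan. Section 2.5 attaches this restriction to PSMA R2, whereas Section 5.2 attaches it to the scan described second, which may be either tracer; these passages must be reconciled.

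The reply does not remove the conflict. Sections 5.3, 10.1, 11.1 and 11.4.2 name PET/MRI as what is read or compared, and nothing excludes MR findings from that read. Nor does settling on uptake suffice: under Section 11.4.1 a lesion seen on MR alone would leave the analysis, so an MR-yes, tracer-no lesion survives only where the other tracer found it.

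**Conclusion.** The concern holds in this form: the only formal comparison has two incompatible index tests in the plan, and the choice between them can decide the sensitivity result. For a PET equal to MR, the chance of a significant sensitivity win is 3.3% on the uptake call, 33% to 92% if half to a tenth of MR-only lesions are discounted, and 99.7% under a full either-positive read. These figures rest on 50 independent malignant lesions, MR at 40% and independent hits. With greater overlap the full either-positive read wins less often (57% or 10% when PET adds 10% or 5% of lesions). Clustering of lesions within men is not modelled and would lower power. This is more than missing detail, because running Section 11.4.2 on the PET/MRI read of Section 11.1 can bias the only formal test. Separately, "A sample size of 50 patients will provide 90% power at one-sided 5% error to detect such a difference" does not carry over to the paired uptake test unless MR-only lesions are about 2% to 3% of the total.

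**What to change.** - In Sections 10.1, 11.4 and 11.4.2, name the index test, per tracer, as the uptake call of Section 11.4, with MR used for localisation only, tested against the blinded MR-alone call of Section 10.2. Word Sections 5.3 and 11.1 to match.
- Extend the Section 11.4.1 analysis set to include lesions seen on MR alone. Without this the uptake-only test stays tilted.
- Report combined PET/MRI as confirmed lesions added to MR and false positives added to MR, with confidence intervals and no superiority test against its own component.
- Restate the Section 11.5 power for the paired test with a stated discordance. At 60% against 40%, with 50 independent lesions and one-sided 5%, it is about 57% (exact) to 63% (approximate) if the reads are independent.
- Reconcile Sections 2.5 and 5.2 on which session is limited to attenuation-correction MR.

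The cost is mainly wording, since both component reads are already planned. There are two downsides: the combined figure carries no p-value, and the stated power becomes less favourable.

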#### **11.5 Sample size justification**

The following estimate is for a per-lesion analysis. We expect approximately 70% of patients (~35) to have one or more PET-positive findings and approximately 1/3 to be biopsied. Our existing data for  $^{68}\text{Ga}$  PSMA-11 and  $^{68}\text{Ga}$ -RM2 (please see attached publications) indicate no false positive findings based on biopsy. We cannot predict an average number of lesions per patient given small data available to date, but if only half of the positive patients have more than one lesion, this will easily yield 50 lesions. We also expect the sensitivity of MR alone to be roughly 40%, while that of PET to be roughly 60% or more. A sample size of 50 patients will provide 90% power at one-sided 5% error to detect such a difference. Participants who complete only one PET/MRI scan (either due to withdrawal of consent or loss to follow-up) will not be replaced with additional subjects.

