### **6.3. Follow-up**

Active subject participation ends after the 24 to 72 hour post-scan Safety Follow-up. Investigators will follow subjects by chart review for 12 months post-scan to record any standard of care biopsies or imaging results. If required by treating physicians for standard of care biopsies, the investigators will assist with identification of lesions that can be biopsied, based on Ga-NeoBOMB1 and/or Ga-PSMA-R2 PET/MRI findings.

If a subject transfers clinical care outside of Stanford Healthcare during the chart review clinical follow-up period, investigators will request permission to contact the treating physician to review medical records.

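### The 90% power in 11.5 treats about 50 PET-positive lesions as if all were confirmed malignant; fewer will probably be evaluable, and no allowance is made

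*Combined protocol and SAP*

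**What the plan says.** Section 11.5 sets the unit of the calculation: "The following estimate is for a per-lesion analysis". It then builds a lesion count. "We expect approximately 70% of patients (~35) to have one or more PET-positive findings", and "if only half of the positive patients have more than one lesion, this will easily yield 50 lesions". It concedes that the multiplicity is unknown: "We cannot predict an average number of lesions per patient given small data available to date". In the same paragraph it expects "approximately 1/3 to be biopsied", without saying whether that is a third of men or of findings. Sensitivity is taken as roughly 40% for MR, "while that of PET to be roughly 60% or more", and 90% power at one-sided 5% is claimed for a sample of 50. That sentence says patients, although the estimate is per lesion.

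Section 11.4 defines a lesion's disease status by biopsy where feasible and otherwise by 12 months of clinical follow-up with imaging. Section 11.4.2 compares the sensitivity of PET/MRI and MR by McNemar's test.

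Under section 6.3, active participation ends 24 to 72 hours after the scan. Investigators then review charts "to record any standard of care biopsies or imaging results". The study calendar in section 7 lists only chart review at 12 months.

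**The concern.** Sensitivity is a proportion of lesions known to be malignant. A PET-positive lesion with neither a biopsy nor adequate follow-up imaging has no disease status and cannot enter the paired test. Section 11.5 nevertheless goes directly from detected lesions to power, and gives no expected share with a reference-standard result.

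Biopsy is expected for about a third. The rest depend on imaging that the trial does not schedule and on records that may sit outside the institution. Men who complete only one scan are not replaced. If a material share of lesions stays unconfirmed, a non-significant PET versus MR comparison would be read against a 90% power that the design does not secure.

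**Working it through.** **Inputs from the documents.** Sensitivities 0.40 and 0.60, so d = 0.20; one-sided alpha 0.05 (z = 1.645); n = 50; about 35 PET-positive men, half of them with more than one lesion (11.5); paired McNemar test (11.4.2).

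**Assumptions.** The documents give neither the discordant proportion pd nor the share of lesions confirmed. The smallest possible pd is the difference itself, 0.20. Independent reads would give 0.6 × 0.6 + 0.4 × 0.4 = 0.52.

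**Lesion count.** If each multi-lesion man has exactly two lesions, the count is 35 + 17.5 = 52.5, or 1.5 per positive man. This is the minimum under the stated assumption. It reaches 50 at 50/1.5 = 33.3 men, which is 67% of 50. With three lesions per multi-lesion man (illustration only) the count is 35 + 2 × 17.5 = 70, and 50 is reached at 25 men, or 50%.

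**Reproducing the 90%.**
- One-sample normal approximation, 60% against a fixed 40%: Φ[(0.2√50 − 1.645√0.24)/√0.24] = Φ(1.24) = 89.3%.
- Asymptotic McNemar: Φ[(d√n − 1.645√pd)/√(pd − d²)]. With pd = 0.25 and n = 50: Φ[(1.414 − 0.822)/0.458] = Φ(1.29) = 90.2%. The required n at this pd is 49.7, so 50.

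Both routes use all 50 units as evaluable.

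**Power by number of confirmed malignant lesions.** The exact figure sums over the number of discordant pairs m, which is binomial(n, pd). For each m it takes the probability that the one-sided 5% binomial test rejects when a share (pd + d)/(2pd) of the discordant pairs favours PET (0.90 at pd = 0.25).

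| Confirmed lesions | pd 0.20, asymptotic | pd 0.25, asymptotic (exact) | pd 0.30, asymptotic | pd 0.52, asymptotic |
|---|---|---|---|---|
| 50 | 95.5% | 90% (88%) | 84% | 63% |
| 44 | 93% | 86% (83%) | 80% | 58% |
| 33 (two thirds of 50) | 85% | 76% (67%) | 69% | 48% |
| 25 (half) | 75% | 65% (49%) | 58% | 39% |
| 17 (one third, biopsy only) | 59% | 50% (25%) | 44% | 30% |

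**Confirmed lesions needed for 90%**, from [(1.645√pd + 1.282√(pd − 0.04))/0.20]²: 39 at pd = 0.20, 50 at 0.25, 61 at 0.30 and 108 at 0.52.

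**Detected lesions needed to leave 50 confirmed:** 75 if two thirds are confirmed, 100 if half, 150 if one third.

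**The case against.** Several counter-arguments have force.

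- *Biopsy is not the only route.* Follow-up imaging is an accepted reference standard, and section 6.3 provides for requesting outside records. A reader might infer that only a third of lesions will be evaluable, or that true power is 25% to 50%. The documents do not support that. One third biopsied is not a ceiling, and the 17-lesion row is a biopsy-only case that the protocol does not plan.
- *The lesion count is a floor.* Section 11.5 allows multi-lesion men more than two lesions. At 70 detected lesions, 71% confirmation would still leave 50. It would therefore be too strong to say that the count has no margin or must fail below 67% PET-positive men. But the plan says it cannot predict lesions per patient, so it cannot count on a surplus either.
- *90% is not an upper limit.* At 20% discordance, 50 confirmed lesions give 95.5% and 39 give 90%, so some loss can be absorbed. PET sensitivity is also put at 60% or more. This favourable case is one end of a range: at 30% discordance even 50 confirmed lesions give 84%.
- *The counted set does not match the model.* Within PET-positive lesions PET cannot have 60% sensitivity. If 52.5 true PET-positive lesions were 60% of all malignant ones, there would be 52.5/0.6 = 87.5, and 57% confirmation would give 50. That is a separate defect in the denominator. Section 11.5 does not count PET-negative lesions, and section 11.4.1 limits the analysis population to lesions identified by PET/MRI.
- *The primary outcome measure in 10.1 is lesions detected per patient*, which needs no confirmation. This limits the consequence. The power claim, however, is made for sensitivity, which does need it.

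**Conclusion.** The concern holds. No sum in 11.5 is wrong, and the 90% can be reproduced, but only if all 50 lesions are evaluable. The design does not secure that, and 11.5 makes no allowance for loss. The number of confirmed malignant lesions is likely to be below the number detected; by how much cannot be derived from the documents.

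At 25% discordance, confirming two thirds of 50 lesions lowers power to 76% (67% exact), and confirming half lowers it to 65% (49% exact). At the most favourable discordance, 90% is kept only down to about 39 confirmed lesions. The exact test should be preferred at small counts: at 17 lesions the asymptotic figure is double the exact one.

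These figures rest on an assumed discordance, an assumed confirmed share and independent lesions. Clustering of lesions within men is ignored, both here and in 11.5.

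**What to change.** Keep 50 patients and restate 11.5 in confirmed malignant lesions. Possible wording: *90% power requires about 50 confirmed malignant lesions assuming 25% discordant pairs (about 39 at 20%).*

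Follow this with the power at about 50%, 67% and 85% confirmation of 50 lesions (25, 33 and 43) over a stated discordance range, using the exact test at the small counts. At 25% discordance and 43 lesions, the formulas above give 86% asymptotic and 82% exact.

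State the share of lesions expected to have a reference-standard result, and say how unconfirmed lesions are handled. Make clear whether the third biopsied refers to men or findings, and whether the 50 in the power sentence means patients or lesions. Drop the word easily. Add that the count falls below 50 at under 67% PET-positive men only if multi-lesion men have exactly two lesions.

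The cost is revised text in one section and a less favourable stated power. No patients, scans or procedures are added.
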